3.2 Randomization

The study is open-label and cohort assignment will be based on current dose level and disease status.

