1 PROTOCOL SUMMARY

1.1 SYNOPSIS

Title: Prospective Randomized Open, Blinded Endpoint (PROBE) Study of AMDX-2011P as a Retinal Tracer in Subjects with Neurodegenerative Diseases Associated with Amyloidogenic Proteinopathy

Study Phase: Phase 1/2a

Study Description: AMDX-2011P is a novel retinal tracer in clinical development for the detection of neurodegenerative diseases associated with amyloidogenic proteinopathy by detecting alpha-synucleinopathies (α -syn) in Parkinson's disease, and transactive response DNA-binding protein 43 (TDP-43) in amyotrophic lateral sclerosis (ALS). Nonclinical studies have demonstrated that AMDX-2011 binds selectively to protein with high beta sheet content, such as retinal α -syn and TDP-43 deposits, enabling visualization through conventional retinal imaging. There is currently a significant need for an accessible diagnostic measure to facilitate early diagnosis and patient management in these conditions.

The current prospective randomized open, blinded endpoint (PROBE) study will evaluate the activity, safety, tolerability, and pharmacokinetics (PK) as well as detect amyloidogenic deposits through retinal imaging following escalating doses of bolus intravenous (IV) AMDX-2011P administration in subjects with Parkinson's disease, multiple system atrophy (MSA) and ALS. Assessments of retinal images will be conducted by central masked assessors in a randomized fashion.

Objectives and Endpoints:

OBJECTIVES	ENDPOINTS
Primary	

 To assess safety and tolerability of single IV dose of AMDX-2011P in subjects with neurodegenerative diseases (Parkinson's disease, MSA and ALS). 	
 Incidence, nature, and severity of adverse events (AEs) and serious adverse events (SAEs).
Secondary	

 To assess the ability of AMDX-2011P to identify α-syn in retina of subjects with Parkinson's disease or MSA. 	
 Detection of α-syn in the retina after AMDX-2011P administration.

 To assess the ability of AMDX-2011P to identify TDP-43 in retina of subjects with ALS. 	
 Detection of TDP-43 in the retina after AMDX-2011P administration.

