4 STUDY DESIGN

4.1 OVERALL DESIGN

This is a PROBE study designed to evaluate safety, tolerability, and the ability of AMDX-2011P to detect amyloid deposits, α -syn and TDP-43 (collectively called amyloidogenic deposits) through retinal imaging, as well as PK of single bolus IV of AMDX-2011P in subjects with Parkinson's disease, MSA and ALS. Study schema is shown in Section 1.2.

The study will enroll up to 4 dose cohorts, as shown in Table 3:

Table 3 Cohorts and Planned Doses

Cohort	Number of Subjects with neurodegenerative diseases (Parkinson's Disease and/or MSA and/or ALS) ^a	Proposed dose level
1	3-9 ^b	25 mg (1 mL)
2	3-9 ^b	50 mg (2 mL)
3	12 ^b	100 mg ^c (4 mL)
4	12 ^b	150 or 200 mg ^c (6-8 mL)

Abbreviation: ALS, amyotrophic lateral sclerosis; SMC, Safety Monitoring Committee; TBD, to be determined.

a. Additional subjects (from any subject population) may be enrolled into any cohort per SMC discretion.

Approximately 9 ALS subjects will be enrolled in the study. Approximately 9 MSA subjects will be enrolled.

b. All cohorts will include 1 sentinel subject who will be observed for 8 hours and evaluated at 24 hours for safety before enrolling the remaining subjects in that cohort.

c. Tentative dose and will be confirmed by SMC based on emerging data from the prior cohorts; intermediate or higher dose level may also be explored in these cohorts.

A Safety Monitoring Committee (SMC), comprised of the Study Medical Monitor (or designee), neurologists with experience in these diseased populations, an ophthalmologist with retinal imaging expertise, and the Sponsor's clinical and technical representatives, will review safety data throughout the study. The SMC may recommend modifying the duration of observation or timing of study procedures based on safety and other available data from the first cohort. For additional details, refer to Section 10.1.5.

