All cohorts will include subjects with neurodegenerative diseases (Parkinson's disease, MSA and/or ALS). The decision to escalate to the next dose level will be made based on review of all available safety and tolerability data collected, including AEs, ECGs, vital signs, and laboratory safety results of the previous dose levels after single dose administration in at least 3 subjects from each cohort. Based on emerging data, additional cohort(s) and/or an intermediary dose may be investigated with prior approval by the SMC. The study may progress to the next cohort if approved upon satisfactory review of available safety data of the previous cohort(s) by the SMC. During each safety review, the SMC will make a decision to either continue enrollment to the next planned cohort, add additional subjects to the current cohort, or change the dose of the next cohort.

Enrollment into each cohort will begin with 1 sentinel subject who will be observed for at least 8 hours at the clinic and evaluated by the investigator at 24 hours following dosing by the investigator. If no safety issues are observed, the remaining subjects will be enrolled into that cohort. Dosing of remaining subjects at the same center will be staggered by at least 1 hour. Dosing within a cohort will continue unless stopping rules are met.

For all dose cohorts, after signing the informed consent, subjects will be screened. If needed, the screening procedures may occur over a period of up to 42 days prior to dosing. On Day 1, subjects will be admitted to the clinical research unit for 8 hours confinement. Eye examination and retinal imaging will be conducted before administration of the study drug. AMDX-2011P will be administered through a single IV bolus injection followed by repeated retinal imaging and PK and safety assessments as outlined in the Schedule of Activities (SoA; Section 1.3). On Day 8 (end of study), there will be a follow-up visit for retinal imaging and safety assessments.

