6.3 MEASURES TO MINIMIZE BIAS: RANDOMIZATION AND BLINDING

This study is open-label, assessor masked. All retinal images will be sent in batches to a central reading center for masked assessment. Assessors will be masked to type of subjects, their disease status, dose, and sequence of post-injection images. Investigators will not be masked to study drug. Please see Section 8.1.4 for further details on the central reading center procedures.

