8.1.4 Central Retinal Image Center (CRIC)

All acquired images will be checked for quality, and subjects' identifiers will be removed by study personnel at investigational site. Deidentified images will be sent to a central imaging center specialized in assessing retinal images for detection and quantification of hyper-fluorescent puncta. Each assessor at the CRIC will be masked to the subject's disease status and sequence of post-injection images. Images will be batched and read at time of the interim analysis and final analysis, or more frequently at the request of SMC. Upon receiving deidentified images from the clinical site, quality assurance (QA) officer at the CRIC will review all images to confirm that the images sent meet the quality, quantity, and image acquisition criteria defined in the protocol. The QA officer will confirm that the images are labeled appropriately and that they were obtained by a certified imager. Once the QA officer reviews and confirms the integrity of each image batch, the images will be randomized and submitted to the masked assessors for grading. At the time of the interim and final analyses, the randomized masked images submitted to the assessors will be evaluated for image quality and for the number of distinct hyper-fluorescent puncta. Additional information will be provided in the imaging section of the Study Reference Manual.

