6.8 Secondary Analysis

The number, diameter, and area of post-injection hyper-fluorescent puncta detected on fundus fluorescence images upon injection of AMDX-2011P that were not present prior to injection will be summed and descriptive statistics will be presented for each study eye per neurodegenerative disease population (e.g PD, ALS, MSA, CAA) and dose levels.

- Detection of α-syn in the retina after AMDX-2011P administration, defined as the number of distinct new spots that are visible to the naked eye post-injection only.
- Detection of TDP-43 in the retina after AMDX-2011P administration, defined as the number of distinct new spots that are visible to the naked eye post-injection only.

- Detection of Amyloid Beta in the retina after AMDX-2011P administration, defined as the number of distinct new spots that are visible to the naked eye post-injection only.
- PK parameters of AMDX-2011P and AMDX-2011 calculated from concentrations in plasma.

Diagnostic test summary statistics will be presented overall. Calculated values will include:

- A true positive diagnosis is defined as detection of hyper-fluorescent puncta on fundus fluorescence imaging that were not present prior to injection of AMDX-2011P.
- A false negative is defined as an eye from a subject with definite diagnosis and no new hyper-fluorescent puncta detected post-injection of AMDX-2011P via fundus fluorescence imaging that were not present prior to injection.

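### Subjects are not randomised and no disease mix is set per dose cohort, so any sensitivity not reported by dose within disease carries whatever dose mix was enrolled

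*SAP*

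**What the plan says.** **Randomisation.** The title in Protocol 1.1 begins "Prospective Randomized Open, Blinded Endpoint (PROBE) Study of AMDX-2011P as a Retinal Tracer". Protocol 6.3, the section on randomisation and blinding, says "This study is open-label, assessor masked" and describes no allocation of subjects. SAP 3.2, headed Randomization, says "The study is open-label and cohort assignment will be based on current dose level and disease status" but not how disease status is used. What is randomised appears in Protocol 8.1.4: after quality checks, "the images will be randomized and submitted to the masked assessors for grading".

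**Disease mix.** Protocol 4.1 and Table 3 let each cohort hold Parkinson's disease, MSA and ALS in any combination. Note a to Table 3 adds: "Additional subjects (from any subject population) may be enrolled into any cohort per SMC discretion". Numbers by disease exist only for the study as a whole:
- MSA: about 9 (Protocol 4.1, SAP 3).
- ALS: about 9 (Protocol 4.1, SAP 3), but about 12 in the synopsis and in Protocol 9.1.
- Parkinson's disease: none given.

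**Cohort sizes and doses.** Table 3 plans 3-9 subjects at 25 mg, 3-9 at 50 mg, 12 at 100 mg and 12 at 150 or 200 mg, with the last two doses tentative. The protocol caps the total at 36.

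**Reporting.** SAP 6.8 summarises new puncta by disease population and dose level. For the diagnostic results it says "Diagnostic test summary statistics will be presented overall". Protocol 9.3.1 promises the sample-size variables for the pooled populations and for each disease.

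**The concern.** In an escalation study, dose follows calendar time. If the diseases are not enrolled evenly over time, a difference in detection between diseases may be a difference in dose, and the reverse. The protocol itself gives a reason to expect differences between diseases: Section 2.2.2 says that MSA deposits lie almost exclusively in a cell type absent from the retina, and that fluorescence profiles may differ by disease.

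The comparisons will be used. SAP 7 lists puncta counts per subject at the interim analysis, partly to inform the choice of dose. SAP 6.10 looks at puncta between cohorts, and Protocol 9.3.3 summarises puncta per cohort with the diseases together.

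A sensitivity averaged over low and high doses could be read as the tracer's performance when it belongs to no single dose. The word *Randomized* in the title suggests a protection against this that the design does not have.

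**Working it through.** **The plan's own figure.** SAP 3.1 states a sensitivity of at least 0.8, assuming 10% false negatives and prevalence of 0.5 per disease and 0.75 pooled. It follows from sensitivity = 1 − (false-negative share ÷ prevalence):
- per disease: 1 − 0.10/0.50 = 0.80
- pooled: 1 − 0.10/0.75 = 0.867

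Dose does not enter, so the plan gives no expected sensitivity by dose. All dose-specific and disease-specific sensitivities below are assumptions.

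**Pooled figure and cohort size.** Assume 0.3 at 25-50 mg and 0.9 at 100 mg or above, in every disease. Cohorts 3-4 hold 24 subjects (Table 3) and Cohorts 1-2 hold n. Pooled sensitivity = (0.3n + 0.9 × 24)/(n + 24).
- n = 6: (1.8 + 21.6)/30 = 0.78
- n = 12: (3.6 + 21.6)/36 = 0.70

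Both fit Table 3 and the cap of 36. What moves the result here is the size of the low-dose cohorts, not which disease sat where.

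**Disease-specific figure and dose mix.** Keep the same assumptions, with n = 12 and 9 ALS subjects. An even spread puts 9 × 12/36 = 3 of them at low dose.

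| ALS at low dose | ALS sensitivity |
|---|---|
| 1 | (0.3 + 7.2)/9 = 0.83 |
| 3 | (0.9 + 5.4)/9 = 0.70 |
| 5 | (1.5 + 3.6)/9 = 0.57 |

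The tracer is the same in each row. Only the enrolment pattern differs.

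**A milder dose effect.** Assume 0.50, 0.70, 0.90 and 0.95 for Cohorts 1 to 4, cohorts of 6/6/12/12, and Parkinson's disease/ALS/MSA totals of 18/9/9.
- ALS or MSA, lowest: (6 × 0.50 + 3 × 0.70)/9 = 0.567. Highest: all nine in Cohort 4, 0.95.
- Parkinson's disease, lowest: (6 × 0.50 + 6 × 0.70 + 6 × 0.90)/18 = 0.70. Highest: (12 × 0.95 + 6 × 0.90)/18 = 0.933.
- Pooled, any allocation: (3.0 + 4.2 + 10.8 + 11.4)/36 = 0.817.

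**Dose-specific figure and disease mix.** Assume no dose effect, with MSA at 0.6 and the other two diseases at 0.9. A 100 mg cohort of 12 then shows 0.90 with no MSA subjects and (9 × 0.6 + 3 × 0.9)/12 = 0.675 with nine. The pooled value stays at (27 × 0.9 + 9 × 0.6)/36 = 0.825.

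**When the pooled figure depends on who received which dose.** This needs a dose effect that differs by disease. Assume MSA at 0.1, 0.2, 0.7 and 0.9 over the four cohorts, and the others at 0.8, 0.9, 0.9 and 0.9. The pooled figure then runs from 25.5/36 = 0.708 (MSA fills the 25 mg cohort and three places at 50 mg) to 31.8/36 = 0.883 (all MSA in Cohort 4).

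**The case against.** Several points on the other side stand.

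- **The label has a meaning.** The synopsis says image assessment is done in random order, and Protocol 6.3 and SAP 3.2 openly say open-label. The title misleads, but no promised procedure is missing.
- **Part of the remedy is already planned.** Puncta are summarised by disease and dose, sensitivity is promised by disease, each disease is an exploratory subgroup (Protocol 9.3.5), and all data are listed. What is missing is the diagnostic statistics by dose.
- **Nothing inferential depends on it.** SAP 6 plans no formal tests, and the primary endpoint is safety. Descriptive tables can still mislead, but this limits the weight of the point.
- **Allocation detail may sit elsewhere.** The master protocol and the SMC charter were not supplied.

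A reader might also infer more than the documents support.

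- *That dose and disease are confounded.* They can be. A balanced mix is equally permitted, and the study-level targets limit the imbalance somewhat.
- *That ALS is likely to miss the higher doses.* Table 3 fixes 24 places in Cohorts 3-4. If 9 ALS subjects fell at random among 36 places, the chance of 3 or fewer in those 24 is (220 + 11,880 + 218,592 + 1,870,176)/94,143,280 = 2.2%. Enrolment by referral is not a random draw, so this is only a guide.
- *That Cohorts 1-2 could hold 18 subjects.* With 24 in Cohorts 3-4 the total would be 42, above the protocol's cap of 36.
- *That MSA will be enrolled only late, because SAP 7 plans no MSA interim.* The same sentence names a glaucoma group found nowhere else in the plan, so it is weak evidence about enrolment order.
- *That places must be reserved for each disease.* In a first-in-human escalation this could delay the higher cohorts. It is a trade-off for the sponsor, and the reporting problem can be solved without it.

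**Conclusion.** The point holds as a matter of reporting and labelling. Subjects are not randomised, the supplied documents set no disease mix per cohort, and no diagnostic statistic is planned by dose.

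The size depends on a dose effect that the documents do not quantify. Under the assumed 0.3 and 0.9, the pooled sensitivity differs by 0.08 between two permitted enrolments. An ALS figure differs by 0.27 (0.83 against 0.57, unrounded 7.5/9 − 5.1/9) between one and five low-dose subjects out of nine. If sensitivity does not vary with dose, mixing doses does not distort the disease-specific figures.

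The disease-specific and dose-specific comparisons are more exposed than the pooled figure. With cohort sizes and disease totals fixed and additive effects, the pooled figure does not depend on who received which dose.

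**What to change.** 1. **SAP 6.8.** Present true-positive and false-negative counts and sensitivity by dose level within each disease, stating the unit (eye or subject). Give no figure pooled over doses without that table beside it. Cells will be small and some may be empty, and the table should show this.
2. **Title and design statements (Protocol 1.1, 2.1, 4.1, 4.2; SAP 3).** Describe the study as an open-label, non-randomised dose escalation with masked, randomised-order image reading. Label contrasts between doses and between diseases as non-randomised wherever they appear, including SAP 6.10.
3. **SAP 3.2.** State how disease status drives cohort assignment, or say that it does not. Reconcile the ALS target between the synopsis and Protocol 9.1 (about 12) and Protocol 4.1 and SAP 3 (about 9). At 36 subjects with 9 MSA, this decides whether 36 − 12 − 9 = 15 or 36 − 9 − 9 = 18 places remain for Parkinson's disease.

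The cost is table shells and amendment wording. No extra subjects, visits or readings are needed, and enrolment is not slowed.

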3.3 Schedule of Evaluations and Analysis Visit Windows

The schedule of visits and procedures are provided in the study protocol AMDX-2011P-101, Version 5.0, Amendment 5, Section 1.3 and AMDX-2011P-001, Version 1.0, Section 1.3. The study consists of a screening visit, treatment day, and 1 follow-up visit. For purposes of analysis, nominal time points will be used in data summarizations. The following target windows are expected for each visit:

Visit	Target Day of Visit	Visit Window (Days) for Analysis
Screening	-42 to -1	-42 to -1
Treatment (Day 1)	1	1
Follow-up (Day 8)	8	8-14

4 ANALYSIS POPULATIONS

4.1 Safety Population

The Safety (SAF) Population includes all enrolled subjects who receive any amount of study drug. The Safety Population will be used for the safety and exposure analyses.

4.2 Imaging Population

The Imaging (IMG) Population includes all enrolled subjects who receive any amount of study drug and who have at least one set of acceptable color fundus photographs and OCT scans pre-dose and at least 3 acceptable quality fundus autofluorescence images during each of the following imaging sessions: pre-dose, post-dose: 5 minutes to 1 hour. Acceptability of the images will be determined as defined in the Imaging Manual.

4.3 Pharmacokinetic (PK) Population

The Pharmacokinetic (PK) Population includes all enrolled subjects who receive any amount of study drug and who have at least one post-baseline PK measurable samples.

5 STUDY VARIABLES/PARAMETERS

5.1 Primary (Safety) Endpoints

The primary endpoint is defined to be:

- Incidence, nature, and severity of treatment-emergent adverse events (TEAEs)
- Incidence, nature, and severity of serious adverse events (SAEs)

5.2 Secondary Endpoints

The secondary endpoints are defined to be:

- Detection of α -syn (numbers per field) in the retina after AMDX-2011P administration by OCT/OCT A and Fundus Fluorescence
- Detection of TDP-43 (numbers per field) in the retina after AMDX-2011P administration by OCT/OCT A and Fundus Fluorescence
- Detection of Amyloid Beta (numbers per field) in the retina after AMDX-2011P administration by OCT/OCT A and Fundus Fluorescence
- The PK parameters of AMDX-2011P and AMDX-2011 calculated from concentrations in plasma through blood sampling

5.3 Pharmacokinetic Endpoints

The following PK parameters will, where possible, be determined (to a precision minimum of 3 significant figures):

Parameter	Definition
C_0 (ng/mL)	Extrapolated concentration at time equal to zero
C_{max} (ng/mL)	Maximum observed drug concentration
T_{max} (hr)	Time of the maximum drug concentration

Parameter	Definition
AUC _{0-last} (hr*ng/mL)	Area under the drug concentration-time curve (AUC) from time zero to the last measurable concentration.
AUC _{INF} (hr*ng/mL)	AUC from zero extrapolated to infinity
AUC _(0-t)	AUC from time zero to time t
CL/F (L)	Apparent total body clearance following IV administration
t _{1/2} (hr)	Apparent terminal half-life
λz (1/hr)	Apparent terminal elimination rate constant
V _{ss} (L)	Steady-state volume of distribution

6 STATISTICAL ANALYSIS METHODS

No formal statistical tests or inference will be performed. All summaries will be presented using descriptive statistics for each cohort, and overall. Data processing, summarization, and analyses will be performed using SAS Version 9.4 or higher. Unless otherwise discussed, continuous variables will be summarized by the number of available data points (N), mean, standard deviation, median, minimum, and maximum. 90% confidence intervals, least-square means, and ratio for geometrics LS means will be displayed when appropriate. The mean, median, minimum, and maximum will be displayed with the same number of decimals as raw data, and the standard deviation will be displayed with two more decimals than raw data. Categorical variables will be summarized by the number and percentage of subjects in each level, where the denominator for each percentage is the number of subjects in the relevant population and specified cohort. Percentages will be displayed to one decimal place and proportions will be displayed to three decimal places. Data listings of all data collected on the eCRF will be presented, sorted by subject number and visit, where applicable.

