3 STUDY DESIGN

This is a Phase I PROBE basket design study to evaluate safety, tolerability, and the ability of AMDX-2011P to detect amyloid deposits, α -syn, TDP-43, and Amyloid Beta through retinal examination, as well as PK of single bolus IV of AMDX-2011P in subjects with Parkinson's disease, Amyotrophic Lateral Sclerosis (ALS), Cerebral Amyloid Angiopathy (CAA), and multiple system atrophy (MSA). The study contains two sub-studies under separate protocols.

List of sub-studies included in Master Protocol Basket Design:

Study Protocol	Study Population	Protocol Appendix for further details	Dose Levels	Number of Cohorts	Subjects Per Cohort

Study AMDX-2011P-001 Version 1.0	Cerebral Amyloid Angiopathy (CAA)	Section 7.1	50 mg (2mL), 100 mg, 150 or 200 mg (tentative), Cohort 4 (TBD)	4	3-5
Study AMDX-2011P-101 Version 5.0, Amendment 5.0	Amyotrophic Lateral (ALS) / Parkinson's Disease, Multiple System Atrophy (MSA)	Section 7.2	25 mg (1mL), 50 mg (2mL), 100 mg (4 mL), 150 mg or 200 mg (6-8 mL)	4	3-9 for cohorts 1-2, 12 for cohorts 3-4

Approximately 9 subjects will be enrolled in each of the ALS and MSA studies. Additional subjects may be enrolled into any cohort per DSMB recommendation for CAA sub-study and all sub-study cohorts will include 1 sentinel subject who will be observed for 8 hours and evaluated at 24 hours for safety before enrolling the remaining subjects into that cohort. Tentative doses will be determined and confirmed by DSMB based on emerging data from prior cohorts. Additional cohorts may be explored per DSMB recommendations.

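### SAP 6 rounds the mean and median puncta count to whole numbers, which at low counts can hide or exaggerate differences of nearly one punctum between doses or diseases

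*SAP*

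**What the plan says.** SAP section 6 sets a default: "Unless otherwise discussed, continuous variables will be summarized by the number of available data points (N), mean, standard deviation, median, minimum, and maximum". It then fixes the precision: "The mean, median, minimum, and maximum will be displayed with the same number of decimals as raw data". The measure of spread is treated differently, in the second half of that sentence: "the standard deviation will be displayed with two more decimals than raw data".

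The detection endpoints fall under this default. SAP 6.8 says each is "defined as the number of distinct new spots that are visible to the naked eye post-injection only". Protocol 8.1.4 has the masked assessors grade images that are "evaluated for image quality and for the number of distinct hyper-fluorescent puncta". SAP 6.8 states that the number, diameter and area of new puncta "will be summed and descriptive statistics will be presented for each study eye per neurodegenerative disease population", and also by dose level. It gives no decimal rule.

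Only the PK results have their own rule, three significant figures (SAP 5.3 and 6.9). Protocol 9.3.1 sets decimals for percentages and proportions but not for means.

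The cells are small. For the Parkinson's disease, ALS and MSA sub-study, SAP section 3 plans "3-9 for cohorts 1-2, 12 for cohorts 3-4" before any split by disease. For the CAA sub-study it plans 3 to 5 per cohort.

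**The concern.** A count has no decimals in the raw data, so the default prints its mean and median as integers, beside a standard deviation with two decimals. A row can read mean 0, SD 0.51, where the spread is given more precisely than the value it describes.

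SAP section 6 plans no formal tests, so the printed descriptive statistics are the result. SAP 6.8 presents the diagnostic test summary overall only. The puncta summary is therefore the one planned display of imaging activity by disease and dose. If counts are low, a reader who compares doses or diseases on the mean or median sees figures rounded by up to half a punctum each.

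**Working it through.** The plan states no figure to reproduce here. The check applies the display rule to counts at the planned cell sizes. The counts are assumed, and halves are rounded up (the SAP states no convention).

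**1. Differences hidden or exaggerated.** In a cell of n eyes, the mean is total/n. Exactly n consecutive totals round to the same positive integer, so two cells of size n can differ by (n − 1)/n and print alike.

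| n | totals printing as 1 | means | totals printing as 2 | means | hidden difference, (n − 1)/n |
|---|---|---|---|---|---|
| 3 | 2 to 4 | 0.67 to 1.33 | 5 to 7 | 1.67 to 2.33 | 0.67 |
| 5 | 3 to 7 | 0.60 to 1.40 | 8 to 12 | 1.60 to 2.40 | 0.80 |
| 9 | 5 to 13 | 0.56 to 1.44 | 14 to 22 | 1.56 to 2.44 | 0.89 |
| 12 | 6 to 17 | 0.50 to 1.42 | 18 to 29 | 1.50 to 2.42 | 0.92 |

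The reverse also happens. With n = 9, totals of 22 and 23 give means of 2.44 and 2.56, a difference of 0.11, yet they print as 2 and 3. Medians behave likewise: {0, 0, 1, 1} has median 0.5, which prints as 1.

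**2. A printed mean of 0 despite detections.** This needs at least one punctum and a total below n/2. The largest such totals are 1 for n = 3, 2 for n = 5, 4 for n = 9 and 5 for n = 12. With one punctum per positive eye, the standard deviation prints as 0.58, 0.55, 0.53 and 0.51, and the maximum as 1.

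To see how often this could occur, assume Poisson counts with mean μ per eye. The probability is P(1 ≤ X ≤ T) for X ~ Poisson(nμ), where T is the largest total above. The documents give no μ. It can be tied to the planning assumption of about 10% false negatives (Protocol 9.1, SAP 3.1) and to the sensitivity of about 0.8 given there. SAP 6.8 defines a false negative by eye, so I apply both per eye:

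- 10% of eyes with no puncta: μ = −ln(0.10) = 2.30
- 20% of eyes with no puncta: μ = −ln(0.20) = 1.61

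| μ | n = 3 | n = 9 | n = 12 |
|---|---|---|---|
| 0.3 | 37% | 80% | 82% |
| 0.5 | 34% | 52% | 44% |
| 1.0 | 15% | 5.5% | 2.0% |
| 1.61 | 3.9% | 0.13% | 0.01% |
| 2.30 | 0.7% | <0.001% | <0.001% |

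For n = 3 and μ = 2.30, nμ = 6.91 and the probability is 6.91 × exp(−6.91) = 0.0069. The upper rows describe a tracer far weaker than planned: at μ = 0.3, exp(−0.3) = 74% of eyes would show nothing.

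**3. After the change.** With one extra decimal, 0.50 and 1.42 print as 0.5 and 1.4, a total of 5 over 12 eyes prints as 0.4, and {0, 0, 1} prints as 0.3.

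**The case against.** A reader might infer that the SAP will report no activity where there is some. The documents do not support that. The same rule requires the minimum, maximum and standard deviation, so any cell with a detection prints a maximum of at least 1, and a non-zero standard deviation unless all eyes have equal counts. Diameter and area are also summarised, each eye is classified as true positive or false negative, and all eCRF data are listed. As the second table shows, a printed mean of 0 despite a detection is common only at rates well below the planning assumption.

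A reader might also infer that rounded means will drive the choice of dose. The one place where the SAP links puncta to dose selection is the interim analysis (SAP section 7), which uses individual subject listings of the counts.

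Three further points have weight:

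- A disease-by-dose cell of 12 is unlikely. Twelve is a whole cohort across three diseases, and only about 9 ALS and 9 MSA subjects are planned in total.
- SAP 5.2 words the endpoint as "numbers per field) in the retina after AMDX-2011P administration by OCT/OCT A and Fundus Fluorescence". A per-field value could carry decimals, and a sum over the triplicate images and time points would raise the counts. Either would reduce the loss.
- Sampling error is large in such cells. At μ = 2.30 the standard error of the mean is √(2.30/3) = 0.88 for n = 3 and √(2.30/9) = 0.51 for n = 9, so rounding is not the main uncertainty.

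What survives is that the rounding adds an avoidable error of up to half a punctum to each printed mean, and this applies at the planned rate too (means near 2 in the first table).

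**Conclusion.** The point holds as a reporting-precision flaw of low severity. Under SAP section 6 the mean and median of integer puncta counts print as whole numbers, and at a few puncta per eye or fewer this can mask or exaggerate differences between doses or diseases of up to nearly one punctum: 0.67 in cells of 3, and 0.92 in cells of 12. In sparse cells the mean, and often the median, can print as 0 beside a non-zero maximum. At the planned false-negative rate that would be rare.

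This rests on the counts being integers when summarised and, for the probabilities, on Poisson counts and a per-eye reading of the 10%. The planning text speaks of subjects. If a subject counted as positive on either eye and eyes were independent, μ would be 2.30/2 = 1.15 per eye, and the figure for n = 3 would be 3.45 × exp(−3.45) = 11%.

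The calculations and the true-positive/false-negative classification are unaffected. If counts run to tens per eye, the loss is negligible. The same default covers vital signs and ECG intervals, but no harm is shown there.

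**What to change.** In SAP section 6, display the mean and median with one more decimal than the raw data, keep the standard deviation at two more, and show the minimum and maximum as recorded. If the sponsor prefers to leave the general rule alone, add this as an exception in SAP 6.8 for puncta counts. The only cost is the changed phrase and a table-shell format. Data collection, sample size and analysis methods stay as they are.
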